2.4 Potential Risks and Benefits

2.4.1 Potential Risks

Risks to the mother include the following:

- Hemorrhage requiring blood transfusion and/or further surgery due to injury of the abdomen, uterus, placenta, and umbilical cord
- Damage to other maternal organs (bladder, bowel) requiring observation, additional surgery
- Placental abruption
 - in certain cases of maternal vascular compromise due to abruption, a hysterotomy, cesarean section and/or hysterectomy may be required, which would impact future reproductive ability
- Death
- Allergic reaction

- Spinal anesthesia risks
- Chorioamniotic separation
- Premature labor /delivery: associated maternal risks of treatment
- Premature rupture of membranes
- Infection

Risks to the fetus include the following:

Risks related to undergoing a fetal procedure:

- Preterm delivery with gestational age associated risks
- Procedure-related fetal death
- Stillbirth
- Fetal paralysis
- Intravascular absorption of narcotic, atropine, or muscle paralytic medication
- Hemorrhage and/or injury of fetal structures, placenta, and umbilical cord
- Foreign body retention
- Infection

Risks related to embolization:

- Intracranial hemorrhage
- Seizures, epilepsy, or other neurological disorders
- Vessel dissection or perforation
- Allergic reaction
- Non-target embolization of the coil
- Brain ischemia
- Inadvertent vessel thrombosis or occlusion

There is no expected radiation risk, as the procedure will be performed under ultrasonographic guidance.

2.4.2 Potential Benefits

The primary benefit to mothers who enroll in the study will be careful monitoring of the pregnancy and fetus using fetal ultrasonography, echocardiography, and MRI. These are all standard of care for monitoring pregnant mothers with fetuses with VOGM at our institution but may exceed the care offered at the subject's non-specialized outside home institutions.

The primary benefit of fetal embolization of VOGM will be the potential avoidance of parenchymal brain injury, cardiopulmonary failure, and other organ failure, and thus potential lowering of significant risk of morbidity and mortality, compared to neonatal VOGM. A secondary benefit may be to improve prognosis after neonatal treatment, in the event such treatment proves necessary despite fetal intervention.

3 OBJECTIVES

3.1 Study Objectives

Primary objective: To evaluate the prenatal safety of fetal embolization for patients with vein of Galen malformations.

Secondary objective: To evaluate the efficacy of fetal embolization for patients with vein of Galen malformations.

3.2 Study Outcome Measures

Primary (safety) endpoint: The procedure is deemed safe if

- 1) **None** of the following unacceptable events occur within 7 days of fetal embolization:
 - a) Fetal death
 - b) Fetal intracranial hemorrhage, either parenchymal or extra-axial, other than petechial hemorrhage. A petechial hemorrhage is seen as focal staining of the brain parenchyma by blood products on MRI, is not associated with mass effect, and there are minimal neurologic sequelae. Petechial hemorrhages are usually considered non-serious adverse events in trials.
 - c) Maternal death
- 2) **None** of the following unacceptable events occur between fetal embolization and delivery:
 - a) Intra-procedural and post-procedural morbidity to the fetus and mother, probably related to the fetal intervention, e.g. placental abruption with subsequent sequelae
 - b) Preterm delivery < 28 weeks, probably related to the fetal intervention
 - c) Maternal blood transfusion or unanticipated surgical intervention, probably related to the fetal intervention
 - d) Presence of fetal imaging evidence of new brain injury in a location or pattern unexpected for the natural history of vein of Galen malformation, probably related to the fetal intervention

Secondary (efficacy) endpoint: The procedure is deemed efficacious if **none** of the following serious postnatal events occur within 30 days of birth:

1. Urgent neonatal embolization is needed. Without fetal intervention, we'd expect 80% of the cohort to require such intervention.
2. Neonatal death. Without fetal intervention, we'd expect a mortality rate of 40% in this cohort.
3. Brain MRI within the first three weeks after birth reveals parenchymal brain injury (acute infarct or gliosis) affecting > 10% of the supratentorial brain volume. Without fetal intervention, we'd expect 30% of patients in this cohort to show this kind of injury.

Additional efficacy data to be collected includes assessment of the neurocognitive development in the treated cohort. Subjects will be followed and assessed until age 24 months and results will be compared to historical controls of NAR VOGM patients treated using the current neonatal paradigm.

Comparison of outcomes will be made with published (meta-analysis and UK national data [1, 2, 6, 7]) and institutional historical results for fetuses who receive standard neonatal or post-neonatal treatment.

Historically, there has been a dearth of detailed data collected for long-term neurocognitive developmental outcomes for the VOGM patient population. Based on historical data that is available, we expect 30% of patients to survive with good neurological outcomes – these data will be used as a comparator to broadly assess outcomes with this intervention. The detailed data from the neurodevelopmental assessments used in this research will be analyzed as an exploratory outcome.

Technical procedural variables to be collected for the study include:

- a) Time for fetal positioning
- b) Time to navigate from the torcular to the prosencephalic varix
- c) Vessel perforation by wire, microcatheter, or coil
- d) Number of coils deployed
- e) Change in color Doppler appearance of varix after embolization
- f) Change in arterialization of waveform within the varix after embolization
- g) Technical fetal embolization procedure success, with time recorded at embolization procedure completion
 - 1. Technical procedural success will be defined as any fetal vein of Galen embolization procedure in which a microcatheter is successfully positioned in the prosencephalic varix and the pre-planned number of detachable coils is deployed.

Additional exploratory outcome measures to be categorized (as absent, mild (i.e. radiographic finding without current clinical impact) or severe) include:

- a) Development of new parenchymal brain injuries on fetal MR
- b) Growth of brain ventricles or extraaxial CSF spaces on fetal MR or ultrasound
- c) Worsening of echocardiographic measures of LV and RV function
- d) Development or worsening of sonographic findings including pleural effusions, pericardiac effusions, and hydrops
- e) Incidence of non-petechial fetal intracranial hemorrhage (either parenchymal or extra-axial)

Neonatal parameters

- a) Postnatal accrual of new parenchymal brain injuries on MR
- b) Neonatal demise

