5.1 Subject Inclusion Criteria

In order to be eligible to participate in this study, an individual must meet all of the following criteria:

1. *Pregnant woman carrying a fetus harboring a vein of Galen malformation in whom the straight sinus or falcine sinus draining the prosencephalic varix measures 7 mm or more on fetal MRI (medio-lateral diameter measured at the narrowest point of the sinus along the rostral-caudal axis, assessed on a T2-weighted coronal slice).*
2. *Fetal gestational age between 23 weeks and term as determined by clinical information and evaluation of first ultrasound.* Although it is believed that the VOGM forms between gestational weeks 6-11 (the developmental window during which the prosencephalic vein of Markowski is present before involution [17]), diagnosis of the condition by fetal ultrasound has never been reported prior to 22 weeks, likely because of the small size of the varix prior to that point. In principle, embolization of the malformation at any time after identification and prior to delivery could forestall the development of brain, cardiopulmonary, and other organ injury. The presence of the low-pressure placental circulation and the fetal lower-flow baseline cerebral circulation might be protective, in terms of reducing potential morbidity from intracranial hemodynamic shifts that accompany embolization. The suitability for fetal treatment, in terms of technical/positional factors, will be assessed on a case-by-case basis by the MFM, ultrasonographer, and neurointerventionalist participating in the study.
3. *Anatomic diagnosis of fetal vein of Galen malformation.* Various cerebrovascular conditions, such as dural sinus malformation and pial arteriovenous fistula, can result in dilated intracranial vascular structures being visualized in utero. Similarly, fetal dilatation

of the vein of Galen can occasionally be seen without the presence of an arteriovenous lesion at all, as a benign venous variant. This condition is readily distinguishable sonographically from VOGM by virtue of the presence of dilated arterial feeding pedicles, and by the presence of an arterial waveform within the varix. This study is aimed solely at fetuses with an established diagnosis of vein of Galen malformation.

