11.3 Safety Review

Two-stage design for safety endpoint

In Stage 1, up to 11 evaluable patients will be enrolled (**Table 2**). Out of 11 patients, if 3 or more patients experience an unacceptable event (see definition in Section 3.2 above and recapitulated below Table 2), the intervention is unsafe and not worthy of further study. If 2 or fewer experience any unacceptable event, the trial will proceed to Stage 2, where an additional 9 evaluable patients will be enrolled, for a total of $N=20$ evaluable patients. Out of $N=20$ patients, if 4 or more patients experience any unacceptable event, the intervention is unsafe and not worthy of further study. If 3 or fewer patients experience any unacceptable event, the intervention is sufficiently safe and worthy of further study. In addition, in case of a single maternal death, the study will be halted pending review by the DSMB and the FDA.

This design tests the null hypothesis that the rate of unacceptable events is $P > 30\%$ versus the alternative that $P < 5\%$. The total type I error rate is 0.097 and the power is 97.5%. If the intervention is truly unsafe, there is a 68.7% probability of early trial termination.

Table 2: Decision rules for safety based on the optimum two-stage design.

	Cumulative number of patients with unacceptable events	Decision
Stage 1: Enroll 11 patients	3 or more	Terminate the trial: agent not worthy of further study
	2 or fewer	Inconclusive result: proceed to Stage 2
Stage 2: Enroll 9 additional patients	4 or more	Terminate the trial: agent not worthy of further study
	3 or fewer	Trial concludes: agent worthy of further study

- 1) Unacceptable events within 7 days of fetal embolization include:
 - a) Fetal death
 - b) Fetal intracranial hemorrhage, either parenchymal or extra-axial, other than petechial hemorrhage. A petechial hemorrhage is seen as focal staining of the brain parenchyma by blood products on MRI, is not associated with mass effect, and there are minimal neurologic sequelae. Petechial hemorrhages are usually considered non-serious adverse events in trials.
 - c) Maternal death
- 2) Unacceptable events occur between fetal embolization and delivery include:
 - a) Intra-procedural and post-procedural morbidity to the fetus and mother, probably related to the fetal intervention, e.g. placental abruption with subsequent sequelae
 - b) Preterm delivery < 28 weeks, probably related to the fetal intervention

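### The 7-day safety window can run past birth, but its offspring events are fetal only, so a procedure-related death or intracranial hemorrhage arising after birth and before day 7 is outside the primary safety count

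*Combined protocol and SAP*

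**What the plan says.** **Eligibility.** Section 5.1 requires "Fetal gestational age between 23 weeks and term as determined by clinical information and evaluation of first ultrasound". No minimum interval between embolization and expected delivery is set. Section 2.4.1 lists premature labor, membrane rupture and "Preterm delivery with gestational age associated risks" among the risks, and Section 7.4 foresees early delivery in some cases.

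**Safety endpoint (Section 3.2, repeated in 11.3).** There are two groups of events on two clocks.
- Group 1: none "of the following unacceptable events occur within 7 days of fetal embolization". Section 11.3 introduces the same list with "Unacceptable events within 7 days of fetal embolization include". The items are (a) fetal death, (b) "Fetal intracranial hemorrhage, either parenchymal or extra-axial, other than petechial hemorrhage" and (c) maternal death.
- Group 2: none "of the following unacceptable events occur between fetal embolization and delivery". Item 2a is "Intra-procedural and post-procedural morbidity to the fetus and mother, probably related to the fetal intervention". Item 2b is delivery before 28 weeks, 2c is maternal transfusion or unanticipated surgery, and 2d is new brain injury on fetal imaging. All four carry a probable-relatedness qualifier.

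**Timing.** Section 11.5 observes safety from Day 0 to Day 7 without mentioning birth, although it also calls the safety events prenatal.

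**Efficacy endpoint (Section 3.2).** Failure within 30 days of birth is urgent neonatal embolization, neonatal death, or "Brain MRI within the first three weeks after birth reveals parenchymal brain injury (acute infarct or gliosis) affecting > 10% of the supratentorial brain volume".

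**The concern.** Group 1 exists to catch acute harm from the procedure. Its clock is tied to embolization, and for maternal death it runs through delivery. For the offspring, the word fetal closes it at birth. That matters for subjects treated late in pregnancy and for those in whom the procedure brings on delivery.

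The safety rule is tight: 3 events in 11 stop the trial and 4 in 20 declare the procedure unsafe. Exactly at a boundary, one subject left out of the count changes the decision.

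**Working it through.** **1. Where each post-birth event lands.** Take an infant born before day 7 after embolization.

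| Event before day 7 | Safety rule | Efficacy rule |
|---|---|---|
| Death after birth, procedure-related | Not 1a (not fetal); group 2 has closed | Counts as neonatal death |
| Non-petechial bleed arising after birth, infant survives | Not 1b (not fetal); not 2d (fetal imaging) | Hemorrhage is not named; counts only if urgent embolization or infarct/gliosis above 10% also occurs |
| Bleed that began in utero, first seen on the postnatal MRI | Can be read as 1b, which has no fetal-imaging requirement; the text does not say | As the row above |
| Bleed seen on the 3-6 hour ultrasound or the 24-28 hour fetal MRI (Section 6.5) | Counts under 1b | Not needed |

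The first two rows are the gap. The third is an ambiguity.

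**2. Weight of a death moved from safety to efficacy.** Stage 1 stops at 3 of 11 for safety (Table 2) and at 6 of 11 non-responders for efficacy (Table 3). The final limits are 4 of 20 and 10 of 20. A procedural death counted only under efficacy therefore carries much less weight.

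**3. The plan's own figures.** Inputs from Section 11.3: n1 = 11, proceed if 2 or fewer; n2 = 9, declare safe if 3 or fewer of 20; null rate 30%, alternative 5%.

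P(declare safe | p) = sum over x = 0, 1, 2 of P[Bin(11, p) = x] × P[Bin(9, p) ≤ 3 − x]

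At p = 0.30: 0.0198 × 0.7297 + 0.0932 × 0.4628 + 0.1998 × 0.1960 = 0.0144 + 0.0431 + 0.0392 = 0.0967 (plan: 0.097).

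At p = 0.05 the result is 0.9755 (plan: 97.5%). Early termination at 0.30 is P[Bin(11, 0.30) ≥ 3] = 0.6873 (plan: 68.7%). All three reproduce.

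**4. Illustration of leakage.** The documents give no rate for post-birth events inside the window, so m below is an assumption. Suppose the true rate of procedure-related unacceptable events, counting both sides of birth, is 30%, and m percentage points go uncounted. The rule then sees p = 0.30 − m/100.

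| m (points) | Counted rate | P(declare safe) | P(stop at Stage 1) |
|---|---|---|---|
| 0 | 30% | 0.0967 | 0.6873 |
| 2 | 28% | 0.1330 | 0.6335 |
| 5 | 25% | 0.2058 | 0.5448 |

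**5. Cost of extending without attribution.** Section 3.2 expects 40% mortality in this cohort without fetal intervention, while the safety alternative is 5%. If unattributed neonatal events added 2 or 4 points (assumed) to a true 5%, P(declare safe) would fall from 0.9755 at 5% to 0.9364 at 7% or 0.8765 at 9%. Any extension past birth therefore needs a relatedness qualifier.

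**The case against.** The strongest reply is that the split is deliberate. The primary objective in Section 3.1 is prenatal safety, and Section 11.5 contrasts prenatal safety events with postnatal efficacy events, each with its own stopping rule. That explains the word fetal. It does not explain a clock that runs 7 days from embolization with no stop at birth, when group 2 shows that the authors wrote delivery where they meant delivery. If the cut at birth is intended, the plan should say so.

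A reader might go further and infer three things that the documents do not support.
- *Any bleed found after birth is excluded.* Only 2d requires fetal imaging. Item 1b does not, so a bleed that began in utero can count whenever it is seen. The scheduled ultrasound and MRI after the procedure should also catch many acute bleeds before birth.
- *Every such subject is missed by the safety count.* Item 2a may capture some of them, for example procedure-related membrane rupture with sequelae. That would be a case-by-case reading, since 2a names the fetus and mother and ends at delivery.
- *Deaths disappear from decision-making.* Neonatal death within 30 days is an efficacy failure under a rule that can stop the trial at once. Neonatal adverse events are recorded (Section 8.1), serious ones go to the DSMB (Sections 8.4 and 9), and Section 5.5 allows termination for unacceptable risk. Postnatal brain injury on MR is also collected as an exploratory measure.

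These safeguards stand, and they narrow the gap. They do not put a post-birth procedural death or bleed into the Table 2 count, which is what decides whether the procedure is called safe.

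**Conclusion.** The point holds in a limited form. Followed as written, the primary safety rule omits a procedure-related death or non-petechial intracranial hemorrhage that arises after birth but within 7 days of embolization. The death is left to the looser efficacy rule. The hemorrhage in a survivor is in neither rule unless another efficacy event accompanies it. For a bleed that began before birth but is first seen afterwards, the text is silent rather than exclusionary.

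The affected subjects are those who deliver before day 7 and also have such an event, not everyone who delivers early. Their number cannot be derived from the documents. The rise from 9.7% to between 13.3% and 20.6% rests wholly on the assumed 2 to 5 uncounted points of a true 30% rate. It shows how sensitive the rule is and is not an estimate of the bias. The stated error rates themselves are correct for the endpoint as defined.

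**What to change.** In Sections 3.2 and 11.3:
- Keep fetal death and fetal non-petechial intracranial hemorrhage as they are. Add to 1a and 1b neonatal death and neonatal non-petechial intracranial hemorrhage within 7 days of embolization, whether or not delivery has occurred, when judged probably related to the fetal intervention. Group 2 already uses that standard.
- State that a hemorrhage first seen inside that window on the postnatal MRI, which Section 7.4 describes as usual care typically on day 1, is assessed under 1b.
- Align the description of safety events as prenatal in Section 11.5.

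The thresholds, sample size and stated error rates stay the same at the same null and alternative rates, and no study procedure is added. The costs are some attribution judgment after birth and the possibility that one death counts under both rules, which the text should acknowledge. After an unplanned delivery elsewhere, the assessment depends on records obtained from that hospital, as Section 5.4.2 already provides.

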7.2 Study Intervention (Visit 2)

Study Procedure Visit

- Perform a preprocedure assessment on the mother
- Obtain clinical procedural consent and anesthesia consent
- Perform the study intervention

After the intervention

- Mothers will be monitored at least overnight at BWH or BCH, or longer if needed
- Tocolytic medication will be administered perioperatively and as needed for the first 12 hours post-intervention
- Fetal heart rate will be monitored continuously after the procedure
- Focused ultrasound to look at cervix, placenta and fetal brain will be performed 3-6 hours post-procedure
- Fetal ultrasound, fetal echocardiogram, and fetal MRI will be performed 24-28 hours after the procedure
- Fetal distress will be addressed clinically and as appropriate for gestational age and status of vein of Galen malformation
- Preterm labor, rupture of membranes and abruption will be addressed clinically, as appropriate for gestational age

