7.3 Pre-Delivery Follow up visits

If more than 4 weeks remain before expected delivery, the following assessments will be repeated every 4 weeks until delivery:

- Fetal ultrasound, fetal echocardiogram, and fetal MRI

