7.4 Delivery

Plans will be made for all subjects to be delivered at BWH. The mode of delivery is not impacted by the fetal intervention and will be determined based on clinical criteria. Likewise, gestational age of delivery will be determined clinically. Depending on the specifics of each case, including how far along the pregnancy is, how severely affected the fetus is, and other factors, in some cases, early delivery would be the chosen option, while in others, termination might be the recommended option, as previously discussed by the subject with the clinical care team. A recommendation of termination of pregnancy would result from major cerebral injury (intracranial hemorrhage other than petechial or parenchymal infarct >10% of the supratentorial brain volume) visualized on fetal imaging, in the setting of a gestational age young enough that termination remains an option. As such major cerebral injury is one of the unacceptable safety events mentioned above in Section 3.2 and below in Section 11.3, the subject in question would be included in the calculations related to the two-stage study design for safety. However, since fetal death would not have been spontaneous but rather by termination of pregnancy, the subject would not be counted towards the fetal deaths in the study.

If no such situation arises, elective delivery will be performed on a date chosen by the obstetrician as optimal in terms of safety for the mother and baby, in the same way that delivery dates are chosen for patients with vein of Galen malformations who do not undergo fetal intervention.

The newborn will be admitted to the NICU, as per the current practice for all patients with VOGM. As per clinical care, an MRI and echocardiogram will be performed as soon as possible after delivery, typically on day 1 of postnatal life. All care, including additional embolization procedures and additional imaging, will be done per standard of care for this patient population. Per our protocol (and similar to that of most major referral centers for VOGM), if a neonatal patient is unable to be extubated or is not stable enough on medications to be discharged from the NICU within a week due to cardiopulmonary failure, this indicates a need for urgent neonatal embolization.

At our center, extubation criteria in neonates without an underlying lung disease include:

- Patient awake with spontaneous and regular breaths, and
- Mean airway pressure on the ventilator < 10 cmH₂O and FiO₂ < 0.25

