 - c) Maternal blood transfusion or unanticipated surgical intervention, probably related to the fetal intervention
 - d) Presence of fetal imaging evidence of new brain injury in a location or pattern unexpected for the natural history of vein of Galen malformation, probably related to the fetal intervention

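### Safety item 2(d) recognises new brain injury only on fetal imaging, so procedure-related injury first seen on the newborn MRI reaches the primary safety count only if it is adjudicated under the general item 2(a)

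*Combined protocol and SAP*

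**What the plan says.** The primary safety endpoint in 3.2 has two groups of unacceptable events. Group 1 covers the first 7 days: fetal death, non-petechial fetal intracranial hemorrhage (1b) and maternal death. Group 2 lists events where none "of the following unacceptable events occur between fetal embolization and delivery". Within group 2, item 2(d) is "Presence of fetal imaging evidence of new brain injury in a location or pattern unexpected for the natural history of vein of Galen malformation", qualified as probably related to the intervention. Section 11.3 repeats it: "Presence of fetal imaging evidence of new brain injury in a location or pattern unexpected for the natural history". Item 2(a) is a general category of probably related morbidity to fetus or mother, with abruption as its example.

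Planned fetal imaging after the procedure is:

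- a focused ultrasound, including the fetal brain, at 3-6 hours (6.5, 7.2);
- "Fetal ultrasound, fetal echocardiogram, and fetal MRI will be performed 24-28 hours after the procedure" (7.2);
- "If more than 4 weeks remain before expected delivery, the following assessments will be repeated every 4 weeks until delivery" (7.3).

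Eligibility is "Fetal gestational age between 23 weeks and term as determined by clinical information and evaluation of first ultrasound" (5.1). After birth, as part of clinical care, "an MRI and echocardiogram will be performed as soon as possible after delivery, typically on day 1 of postnatal life" (7.4).

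Newborn MRI injury appears in two places. Efficacy item 3 counts parenchymal injury "affecting > 10% of the supratentorial brain volume. Without fetal intervention, we'd expect 30% of patients in this cohort to show this kind of injury" (3.2). Postnatal accrual of new injury on MR is also an exploratory neonatal parameter with no decision rule (3.2).

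**The concern.** Item 2(d) runs to delivery, but the only evidence it accepts can end about a day after the procedure. How long a fetus is observed for new brain injury then depends on when it was treated and when it was born. The next routine look at the brain is the newborn MRI, and no safety item refers to it.

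The harm at issue is central. Section 2.2 says that postnatal trans-torcular embolization carried a risk of venous infarction and hemorrhage, and 2.4.1 lists brain ischemia and inadvertent vessel thrombosis among the fetal risks. The safety decision turns on 3 of 11 or 4 of 20 subjects, so one uncounted subject can reverse it. The gap is one-sided: an uncounted event can only move the result toward safe.

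**Working it through.** **1. Which planned fetal scans can feed 2(d)**

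| Subject | Last planned fetal scan | Unimaged until delivery |
|---|---|---|
| 4 weeks or less to expected delivery at treatment | 24-28 h | the rest of the pregnancy |
| More than 4 weeks remaining, but delivered before the first 4-weekly scan | 24-28 h | up to about 4 weeks |
| More than 4 weeks remaining, followed as planned | the latest 4-weekly scan | up to about 4 weeks |

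A fetal scan done for clinical reasons would count, but none is planned in these intervals.

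**2. Where a procedure-related injury first seen on the newborn MRI goes**

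- 2(d): not met, because the evidence is not fetal imaging.
- Efficacy item 3: met only above 10% of supratentorial volume. This is an efficacy failure and does not add to the safety count.
- 10% or less: the exploratory parameter, and the adverse event record if Grade 2 or higher (8.1).
- 2(a): possible by adjudication; newborn imaging is not mentioned.

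**3. The plan's own figures**

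Inputs from 11.3: 11 then 9 subjects; stop at 3 or more of 11; unsafe at 4 or more of 20; null rate 30%, alternative 5%. With p the rate of subjects counted as having an event:

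P(declare safe) = Σ over x = 0, 1, 2 of P[Bin(11, p) = x] × P[Bin(9, p) ≤ 3 − x]

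P(stop at Stage 1) = P[Bin(11, p) ≥ 3]

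At p = 0.30: 0.0198 × 0.7297 + 0.0932 × 0.4628 + 0.1998 × 0.1960 = 0.0144 + 0.0431 + 0.0392 = 0.0967 (stated 0.097). Stage 1 stopping is 0.6873 (stated 68.7%). At p = 0.05 the result is 0.9755 (stated 97.5%). The design figures are correct; the problem is ascertainment.

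**4. Effect of uncounted subjects**

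Let m be the share of affected subjects who go uncounted: their only unacceptable event is brain injury first seen after birth, and it is not taken up under 2(a). The counted rate is 0.30 × (1 − m). The documents give no m, and no distribution of gestational age at treatment, so m is assumed.

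| m (assumed) | Counted rate | P(declare safe) | P(stop at Stage 1) |
|---|---|---|---|
| 0 | 30% | 9.7% | 68.7% |
| 5% | 28.5% | 12.3% | 64.7% |
| 10% | 27% | 15.5% | 60.5% |
| one sixth | 25% | 20.6% | 54.5% |

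**5. The opposite error**

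If counting newborn findings raised the counted rate for an acceptable procedure from 5% to an assumed 8% or 10%, the same formula gives P(declare safe) of 90.9% or 84.0%, against 97.5%.

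**The case against.** The strongest reply is that 2(a) already covers the case. It counts probably related fetal morbidity between embolization and delivery without limiting how it is detected, and nothing makes 2(d) the exclusive rule for brain injury. This stands in part. A reader might infer that injury first seen on the newborn MRI can never be counted; the documents do not support that. What remains is that the item written for brain injury names fetal imaging, while the general item is silent on newborn imaging. Two adjudicators could classify the same case differently.

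A reader might also infer that a bleed arising between 28 hours and Day 7, but found later, is lost. The text does not say so. Item 1(b) has no modality restriction, and no section says that an undated bleed is dropped. Section 7.4 keeps a subject whose pregnancy is terminated for non-petechial hemorrhage on fetal imaging in the safety calculation, without repeating a 7-day limit.

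The boundary also has a rationale. The primary objective is prenatal safety, and 2.2 describes new brain injury accruing in the first days to weeks after birth. Some newborn findings will be disease or postnatal injury. That argues for requiring a judgement of prenatal onset and relatedness, not for disregarding the scan.

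These injuries are not invisible either: plausibly related events of Grade 2 or higher are recorded, and the DSMB reviews all events (8.1). But recording an event does not place it in the count that the stopping rule uses.

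Finally, m applies to all affected subjects, including those with fetal death, transfusion or early preterm delivery, none of which depends on newborn MRI. Large values of m are therefore hard to defend.

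**Conclusion.** The gap in 2(d) is real and follows from the text alone. For subjects with no fetal scan planned after 24-28 hours, and for the last unimaged interval in the others, procedure-related injury first seen on the newborn MRI does not meet 2(d). Injury above 10% of supratentorial volume is at least an efficacy failure; smaller injury reaches a decision rule on imaging grounds only through discretionary use of 2(a).

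The direction is certain and the size is not. At a true rate of 30%, the chance of a false declaration of safety rises from 9.7% by 2.6, 5.8 or 10.9 percentage points at the three assumed shares. None of these is an estimate for this trial.

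Section 11.5 adds a related inconsistency. It says the safety endpoint is observed from Day 0 to Day 7, while 3.2 and 11.3 run group 2 to delivery. If Day 7 governed, later injury would go uncounted even when fetal imaging showed it.

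**What to change.** 1. **3.2 and 11.3, item 2(d).** Replace the imaging clause with: fetal imaging, or the first postnatal brain MRI, shows brain injury that is new compared with the pre-procedure fetal MRI and is judged to have arisen before delivery. Keep the existing conditions on unexpected location or pattern and probable relatedness. Have the DSMB review attribution.
2. **11.5.** Reconcile the Day 0 to Day 7 window with the window to delivery. Keep each subject's safety status open until the first postnatal MRI, where obtained, has been read.
3. **Item 1(b).** Leave it as it is, but state that a hemorrhage found later and judged to have begun within 7 days counts whichever scan shows it. Do not count undated bleeds by default: 1(b) has no relatedness test, so delivery-related or disease-related bleeds would enter the count.

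This uses a scan already done in usual care. Section 11.5 already allows Stage 2 enrollment to be suspended until Day 30 of life, so a typical Day-1 MRI would not lengthen that pause.

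The cost is some attribution calls and a risk of misattribution, whose effect on an acceptable procedure is shown in step 5 of the working. The MRI is also not assured for every infant: 7.4 describes it as clinical care, typically on day 1, and 5.4.2 foresees unplanned delivery elsewhere with only an attempt to collect the data. The plan should say how a subject without that scan is classified.
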